1 BACKGROUND

Prostate cancer is the most common non-cutaneous cancer and among the top three causes of cancer deaths among men in Finland and other Western countries. Burden of health care costs due to the condition rise up to 180 million euros/year in Finland (1).

Androgens are vital for prostate cancer progression, and androgen deprivation therapy is cornerstone in management of advanced or recurrent prostate cancer that is beyond curative treatment. In androgen deprivation therapy (ADT) serum testosterone is lowered either medically or surgically to a level lower than 1,72 $\mu\text{mol/l}$ (50 ng/dl). (2) These prevents activation of androgen receptors in prostate cancer cells, leading to involution of the prostate tumor and metastases, decreased proliferation and increased apoptosis of prostate cancer cells (3,4).

Common side effects of ADT include fatigue, weight gain, muscle loss, decreased libido and erectile dysfunction, amounting to decreased quality of life (5). Low serum testosterone has also been linked with increased risk for type II diabetes and metabolic syndrome (6). Also associations with elevated risk for memory impairment and cardiovascular disease have been proposed (7,8).

Systematic review published in 2012 found strong evidence for improved overall quality of life among ADT-treated prostate cancer patients participating in supervised resistance training. Moderate evidence was found also for improved physical and social well-being. The authors recommended exercise for all prostate cancer patients on ADT and called for further studies comparing supervised and unsupervised exercise (9). A recent randomized trial found equal fatigue reduction and vitality increase both with supervised and unsupervised exercise (10).

2 STUDY GOALS

[figure not shown]
The study compares effects of supervised and unsupervised exercise on plasma lipid parameters (total cholesterol, LDL, HDL and triglycerides) and glucose levels (fasting plasma glucose, glycated hemoglobin), overall quality of life and on average daily exercise activity in men with prostate cancer and under ADT. As secondary outcome we will study effect on continued exercise activity after the intervention, changes in body composition, blood pressure and risk of fractures, castration resistance as well as death due to prostate cancer and due to any cause.

Study hypothesis is that supervised exercise will improve quality of life, lipid and glucose parameters and increase daily exercise activity more than non-supervised exercise. We also expect higher continued exercise activity, greater changes in body composition and blood pressure and lowered risk of fractures and death in the supervised exercise group.

3 STUDY SETTING

This is a randomized, controlled clinical trial. The study aims to recruit 40 men on ADT for prostate cancer. This will be a pilot study to estimate effect sizes in Finnish population to inform further larger trial. For this reason the sample size will be smaller compared to previous studies on the topic (10,11) and no power calculation is performed yet.

Figure: Study flow chart

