5 INTERVENTION

All participants attend introductory lecture, where a urologist informs them about adverse effects of ADT and positive effects of exercise during ADT, exercise instructor gives advice for training both at home and in the gym and nutritional therapist tells about nutrition to overcome adverse effects of ADT and support training.

After the introductory lecture the participants are randomized 1:1 to either the supervised or non-supervised exercise group (Figure). Men in the supervised group participate in progressive group exercise sessions twice a week for total of 12 weeks at the Varala sports academy in Tampere, Finland. Each exercise session includes both aerobic and resistance training targeting all major muscle groups (Additional document I, exercise program). The non-supervised group will exercise independently for 12 weeks according to the instructions given at the introductory lecture. The first control visit will be after this first period of 12 weeks of exercise.

After the first follow-up visit both groups will continue non-supervised exercise for 12 weeks, after which the second control visit will be arranged. Special focus on the second control visit is to see how many in each group has been able to carry on active exercising, i.e. has the intervention promoted long-term change in exercise activity.

Both study groups will be given Polar wrist activity monitors to be used 24 h/day for the entire course of the study.

All participants are asked to fill validated quality of life surveys EORTC QLQC-30 (overall quality of life) and EORTC QLQC-PR25 (prostate cancer-specific quality of life) at baseline and again at 1st and 2nd control visits. Plasma lipid and glucose parameters, blood pressure and body composition will be measured at each of these visits.

At each visit a separate blood sample is taken and stored for future measurement of biomarkers associated with prostate cancer progression, glucose and lipid metabolism and effects of exercise.

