6 QUALITATIVE EVALUATION OF SUBJECTIVE CAPABILITIES AND QUALITY OF LIFE

On each visit a qualitative evaluation will be performed based on individual- and group interviews to evaluate how men find ADT and exercise affecting their quality of life and how they perceive the intervention as a means to increase their physical activity. On the interviews information will be collected on:

1. How men on ADT perceive their quality of life and what is their subjective definition of quality of life?
 - What kind of side-effects they have had from ADT, how they cope with them in everyday life and how cancer, ADT and ADT side-effects have affected their quality of life?
 - What role exercise has had in their lives before prostate cancer and after it, and how the amount of exercise is tied to their perceived quality of life?

2. What kind of opportunities and obstacles of exercise the participants find in their lives?
 - How men in the supervised exercise group think the intervention will affect their exercise activity in the future? Can supervised exercise help to overcome obstacles for exercising?
 - How men in the non-supervised exercise group cope with obstacles for exercise?

Baseline interview, before the study randomization: A group of 10 men are interviewed before randomization to the exercise groups. The goal is to find how participants expect the intervention to affect their activity and quality of life before they know in which group they will participate.

Second interview at the first control visit: Men in the supervised exercise group are interviewed about the role of their group and supervision on their exercise activity and perceived quality of life. Non-supervised group is interviewed how they have managed to follow the given exercise program and how it has affected their quality of life. All men are asked how they think their exercise habits would have differed had they been randomized to the other intervention group. Additionally their views about how they will be able to carry on exercising will be asked.

Third interview at the second control visit: The questions will evaluate how men have carried on with the exercise; have they been able to increase it or has it rather decreased; have the men found that the exercise intervention has affected their quality of life.

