7 STUDY OUTCOMES AND STATISTICAL ANALYSIS

Primary outcomes:

- Daily total activity, measured during the entire course of study with wrist activity monitor in metabolic equivalents of task (MET) units
- Fasting plasma cholesterol, LDL, HDL and triglycerides, measured at baseline and again at the 1st and 2nd control visits
- Fasting plasma glucose and glycated haemoglobin (HbA1C), measured at baseline and again at the 1st and 2nd control visits
- Overall quality of life and prostate cancer-specific quality of life, measured with validated Finnish versions of EORTC QLQ-C30 v.3.0 ja EORTC QLQ-PR25 at baseline and at each control visit

Secondary outcomes:

- Change in daily activity after the end of supervised group exercise intervention; difference compared to the non-supervised group. Measured with wrist activity monitor in MET units
- Body mass composition, bioimpedance-based measurement of lean body mass, fat mass and skeletal mass as percentage of total body mass measured with TANITA MC-780 device

- Blood pressure level, measured at baseline and each control visit
- Subjective effect of exercise on quality of life and perceived adverse effects of ADT, as based on qualitative interviews

Long-term follow-up

The participants are followed via patient files and national health care registries. Outcomes to be followed are:

- Time from baseline to castration resistance (progression of prostate cancer despite ADT as evidenced by constantly rising PSA or radiological disease progression)
- Bone fractures
- Diagnosis of memory impairment
- Diagnosis of diabetes mellitus
- Diagnosis of cardiovascular disease
- Prostate cancer death
- Death due to any cause

Statistical analysis

All comparisons are done between the supervised and non-supervised exercise arms. Medians of daily activity (in MET units) and quantitative quality of life (as points from the EORTC surveys) at baseline and at each control visit are compared with either Mann-Whitney U-test or Student's t-test depending on normality of the data distribution. Difference in medians of plasma lipid parameters and glucose parameters are analyzed similarly.

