Of the secondary outcomes median time to castration resistance and death are compared between the trial arms using Kaplan-Meier analysis and log-rank test. Analysis for risks of castration resistance, death, prostate cancer death, cardiovascular disease, bone fracture and memory impairment will be analysed using Cox regression with months from the study randomization as the time metric. The regression model will be adjusted for the study arm, age at baseline, time between prostate cancer diagnosis and randomization, ADT method and the time on ADT before participating in the trial.

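### The pilot is meant to estimate effect sizes, but Section 7 names only unadjusted tests at each visit; a baseline-adjusted difference with a 95% CI fits that purpose better and is usually more precise

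*Combined protocol and SAP*

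**What the plan says.** Section 3 describes a randomised trial of 40 men, with no power calculation, and gives its purpose as follows: "This will be a pilot study to estimate effect sizes in Finnish population to inform further larger trial".

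For the primary outcomes, Section 7 says that medians of daily activity and of the quality-of-life scores "at baseline and at each control visit are compared with either Mann-Whitney U-test" or Student's t-test, the choice depending on normality. For the laboratory outcomes it adds: "Difference in medians of plasma lipid parameters and glucose parameters are analyzed similarly". It mentions no confidence interval and no baseline-adjusted model for any primary outcome.

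The baseline values are planned. The list of primary outcomes in Section 7 includes "Fasting plasma cholesterol, LDL, HDL and triglycerides, measured at baseline and again at the 1st and 2nd control visits" and "Fasting plasma glucose and glycated haemoglobin (HbA1C), measured at baseline and again at the 1st and 2nd control visits". The two EORTC questionnaires follow the same schedule.

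Covariate adjustment appears once, in the Cox model for the long-term outcomes: "The regression model will be adjusted for the study arm, age at baseline, time between prostate cancer diagnosis and randomization", together with ADT method and time on ADT.

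**The concern.** A pilot whose purpose is to estimate effect sizes should deliver an estimate and its uncertainty for each outcome. Section 7 instead names tests, and a Mann-Whitney p-value gives the designers of the larger trial no effect size. Because the choice of test follows normality, the summary could also differ between outcomes and visits.

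The baseline value is used only in a separate comparison of the arms at baseline and is never linked to the same man's follow-up value. Randomisation makes the unadjusted difference unbiased on average. In a single trial with 20 men per arm, though, a chance difference between arms at baseline carries into the follow-up difference in proportion to the correlation between the two. Including baseline in the model removes most of that noise. At stake is the width of the intervals on which the next trial would be planned.

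**Working it through.** The plan has no precision or power figure to reproduce: 40 is given without a calculation.

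**Inputs**
- 40 men (Section 3), randomised 1:1 (Section 5): n = 20 per arm, N = 40.
- Assumed, because the documents do not state them: two-sided 95% CI, results in SD units with a common SD, complete and roughly normal data.
- Assumed baseline to follow-up correlation r = 0.3, 0.5 or 0.7. It may differ between outcomes.

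**Unadjusted half-width for a mean difference**

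t(0.975, 38) × √(2/20) = 2.024 × 0.316 = 0.640 SD.

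**Baseline-adjusted half-width**

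t(0.975, 37) × √(2/20) × √(1 − r²) × √(1 + 1/(N − 4)). The last factor allows for chance baseline imbalance.

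| r | Without last factor | With last factor | Simulated mean (60,000 pilots) | Gain on 0.640 |
|---|---|---|---|---|
| 0.3 | 0.611 | 0.620 | 0.616 | 0.02 SD (3%) |
| 0.5 | 0.555 | 0.562 | 0.558 | 0.08 SD (12%) |
| 0.7 | 0.458 | 0.464 | 0.461 | 0.18 SD (28%) |

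The simulated mean for the unadjusted interval is 0.636. Coverage of the intervals was 94.8% to 95.2%.

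To match the adjusted precision of 20 per arm, an unadjusted analysis would need about 26 per arm at r = 0.5 (2.009 × √(2/26) = 0.557, against 0.562) or 37 per arm at r = 0.7 (1.993 × √(2/37) = 0.463, against 0.464).

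**Low correlation.** Simulated mean half-widths, adjusted against 0.636 unadjusted, are 0.645 at r = 0, 0.638 at 0.15 and 0.632 at 0.20. The break-even is therefore just below 0.2, and the worst case is an interval about 1% wider.

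**Loss to follow-up (assumed).** With 17 per arm the half-width is 0.70 unadjusted against 0.67, 0.61 or 0.50 adjusted. With 16 per arm it is 0.72 against 0.70, 0.63 or 0.52. The relative gain hardly changes.

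**Skewed laboratory values.** For a log-normal outcome and a true shift of 0.5 SD on the log scale, power is 32% with Mann-Whitney and 36%, 42% or 57% with the baseline-adjusted model on logs.

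**Bounded scores.** In simulated 0–100 scores analysed untransformed, the adjusted interval covered the true difference in 94.8% to 95.1% of pilots. This includes a four-level score with 52% zeros.

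**The same effect seen as imbalance.** For one outcome, the chance that baseline means differ by more than 0.3 SD is 2 × (1 − Φ(0.3/√(2/20))) = 2 × (1 − Φ(0.949)) = 34%. A 0.3 SD imbalance moves the unadjusted follow-up difference by r × 0.3 = 0.09, 0.15 or 0.21 SD on average. This illustrates the variance already counted in the table and is not a further loss.

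**Daily activity is left out of the precision claim.** Section 5 says "Both study groups will be given Polar wrist activity monitors to be used 24 h/day for the entire course of the study" and describes no wear period before randomisation, so the activity baseline may already reflect allocation.

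**The case against.** The strongest reply is that nothing here is wrong. The tests are valid, the small sample is disclosed, a t-test yields a mean difference with a CI directly, and Section 7 forbids neither intervals nor adjustment. That stands, and it is why this is a recommended improvement. It does not answer the point that the stated output of an estimation pilot is a set of tests.

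Second, the benefit depends on a correlation that the documents do not give. At 0.5 the interval is still ±0.56 SD, so the pilot stays imprecise either way. This also stands, and it limits the size of the claim. The case for naming an interval does not depend on r.

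Third, the text does not date the laboratory and EORTC baselines relative to randomisation either. The only baseline assessment it dates is in Section 6: "Baseline interview, before the study randomization: A group of 10 men are interviewed before randomization to the exercise groups". The flow chart, not shown in the text reviewed, may settle the timing. The point stands as a condition: adjustment should use a value taken before randomisation, for every outcome.

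Fourth, Section 7 speaks of medians, while 0.64 SD belongs to a mean difference. A raw difference in medians would have a half-width of about 0.75 SD under normality, so the comparison is conservative. The fix does change the summary from medians to means or ratios, and that belongs among its costs. Student's t-test, already planned, compares means.

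Fifth, part of the power gain on skewed data comes from changing the test. An unadjusted t-test on logs already has about 34% power, against 32% for Mann-Whitney and 36% adjusted at r = 0.3. That is correct. The half-widths carry the argument, not the power figures.

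**Conclusion.** The concern holds. For lipids, glucose, HbA1c and EORTC scores, the analysis named in Section 7 does not state the estimate that Section 3 makes the purpose of the pilot, and it leaves planned baseline data unused. With 20 per arm, baseline adjustment would narrow the 95% CI half-width from 0.64 SD to about 0.62, 0.56 or 0.46 SD at an assumed correlation of 0.3, 0.5 or 0.7. The gain is worthwhile from about 0.5 upward, negligible at 0.3 and absent below about 0.2, where the cost is at most about 1% in width. These figures assume complete, roughly normal data with a common SD and baseline values taken before randomisation. The change should be made, but the planned tests are not invalid without it.

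**What to change.** Amend Section 7 along these lines:

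> For fasting lipids, fasting glucose, HbA1c and EORTC scores, the primary output is the difference between arms at the 1st and at the 2nd control visit, with its 95% CI, from a linear model with study arm and the baseline value of that outcome, taken before randomisation. Triglycerides, and any other strictly positive laboratory outcome named in advance as skewed, are analysed on the log scale and reported as a ratio. EORTC scores are analysed untransformed. Daily activity is adjusted in the same way only if its baseline comes from a wear period before randomisation. Any outcome without a baseline value from before randomisation is reported unadjusted with a 95% CI. Men are analysed in the arm to which they were randomised, and the number without a value at each visit is reported by arm. The SD and the baseline to follow-up correlation are reported. The Mann-Whitney or t-tests are supportive.

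The SD and correlation are included because the larger trial will need them for its sample size.

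The cost is wording, with no extra patients, visits or measurements. If the flow chart does not show that baseline bloods and questionnaires precede randomisation, Section 5 also needs a sentence to date them. Other downsides are a little more analysis work, a check of model fit in 40 men, a summary in means or ratios in place of medians, the need to name skewed laboratory outcomes before the data are seen, and little or no gain where the correlation is low.

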4 INCLUSION- AND EXCLUSION CRITERIA

Inclusion criteria:

- ADT for prostate cancer, regardless of treatment duration
- Willingness to participate in the study; signing of informed consent

Exclusion criteria:

- Unability for physical exertion; ECOG 2 or higher
- High risk for bone fractures as evaluated by the attending clinician
- Non-Finnish speaking; inability to comprehend Finnish

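### Time on ADT is adjusted for in the long-term Cox models but not in the primary comparisons, and no stratification on it is described: a modest, avoidable loss of precision in a 40-man pilot

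*Combined protocol and SAP*

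**What the plan says.** All references are to the combined protocol and SAP.

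- Section 4 makes eligible any man on "ADT for prostate cancer, regardless of treatment duration". No minimum or maximum duration is set.
- Section 3 gives the size, "The study aims to recruit 40 men on ADT for prostate cancer", and the purpose: "This will be a pilot study to estimate effect sizes in Finnish population to inform further larger trial". It adds that "no power calculation is performed yet".
- Section 5 describes the allocation: "After the introductory lecture the participants are randomized 1:1 to either the supervised or non-supervised exercise group". No stratification, blocking or minimisation is mentioned.
- Section 7 states that daily activity and quality-of-life scores at baseline and each control visit "are compared with either Mann-Whitney U-test or Student's t-test depending on normality of the data distribution". Lipids and glucose measures are handled in the same way. None of these tests carries a covariate.
- Section 7 also specifies Cox models for castration resistance, death and other long-term events. Their covariates include "ADT method and the time on ADT before participating in the trial", together with age and time since diagnosis. No primary outcome is analysed by these models.

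**The concern.** The plan treats time on ADT as worth adjusting for, but only in the long-term event analyses, where 40 men will give little information. It leaves the variable out of the comparisons that the pilot exists to deliver.

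Section 1 gives a reason to expect that time on ADT matters for those comparisons. It attributes weight gain, muscle loss and poorer quality of life to ADT, and links low testosterone to diabetes and metabolic syndrome. These overlap with the primary outcomes on quality of life and glucose and, less directly, on lipids. A man who has just started ADT and a man years into it may therefore differ on these measures, at entry or in their later course.

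Two things are at stake. Variation due to time on ADT stays in the error term and widens the intervals around the effect sizes. In addition, the single allocation that the pilot produces may by chance place more recent starters in one arm, and the estimate carried into planning the larger trial would then be partly a difference in ADT history.

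**Working it through.** The plan gives no power, SD or effect size, so there is no figure of its own to reproduce.

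**Inputs from the documents:** 40 men allocated 1:1, hence 20 per arm (sections 3 and 5); unadjusted two-group tests (section 7).

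**Assumptions, since the documents give no figure:** a share f of recent starters of 20-40%, and a gap g between recent starters and long-term users of 0.5-1.0 within-group SD in the outcome as analysed.

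**Step 1: chance imbalance.** With K recent starters among 40 men, the number x in one arm of 20 is hypergeometric (40, K, 20). The arms then differ by |2x − K| men.

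| f | K | P(differ by ≥ 4 men, 20 points) | P(differ by ≥ 6 men, 30 points) |
|---|---|---|---|
| 20% | 8 | 0.235 | 0.044 |
| 30% | 12 | 0.301 | 0.082 |
| 40% | 16 | 0.333 | 0.105 |

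**Step 2: what an imbalance would do.** The shift in the arm difference is imbalance × g. For 20 points it is 0.20 × 0.5 = 0.10 SD to 0.20 × 1.0 = 0.20 SD. For the root-mean-square imbalance at K = 12 (0.147), it is 0.07 to 0.15 SD. For comparison, the standard error with 20 per arm is √(2/20) = 0.316 SD, and the 95% half-width is about 0.64 SD.

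**Step 3: type I error.** With 12 recent starters, a 1.0 SD gap and no treatment effect, 20,000 simulated randomisations gave a rejection rate of 4.8% for the unadjusted t-test at the 5% level. Given an imbalance of 20 to 30 points, the rate is about 6% to 14% across the assumed gaps, but such allocations are offset by the others.

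**Step 4: precision.** With within-group variance 1, the total variance is 1 + f(1 − f)g². The share explained is R² = f(1 − f)g² / (1 + f(1 − f)g²). The interval narrows by 1 − √(1 − R²), and the equivalent unadjusted sample is 40 / (1 − R²).

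| f | g | f(1 − f)g² | R² | Unadjusted SE | Narrowing | Equivalent N |
|---|---|---|---|---|---|---|
| 20% | 0.5 | 0.040 | 0.038 | 0.322 | 1.9% | 41.6 |
| 20% | 1.0 | 0.160 | 0.138 | 0.341 | 7.2% | 46.4 |
| 30% | 0.5 | 0.0525 | 0.050 | 0.324 | 2.5% | 42.1 |
| 30% | 1.0 | 0.210 | 0.174 | 0.348 | 9.1% | 48.4 |
| 40% | 0.5 | 0.060 | 0.057 | 0.326 | 2.9% | 42.4 |
| 40% | 1.0 | 0.240 | 0.194 | 0.352 | 10.2% | 49.6 |

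**Step 5: adjustment without stratification.** Step 4 takes the arms as balanced on the factor. If they are not, adjustment multiplies the variance by 1/(1 − r²), where r is the correlation between arm and factor. Over randomisations r² averages 1/39 = 0.0256 (at K = 12: 0.147² × 0.25 / 0.21 = 0.0257). The standard error then grows by a factor of about 1/√0.9744 = 1.013. The narrowing becomes 1 − 0.981 × 1.013, about 0.7%, at the low end and 1 − 0.898 × 1.013, about 9%, at the high end.

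**The case against.** **Randomisation already covers this.** The expected shift is zero, and the ordinary interval allows for chance imbalance. This stands. A reader might infer that mixing ADT durations biases the primary comparison. The documents do not support that, and step 3 shows the overall error rate staying near 5%.

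**The time course is not in the documents.** Section 1 names side effects and associations but gives no onset, plateau or size, and no explicit lipid effect. This stands too. The share of recent starters and the gap are both assumptions, and the low end of the range is a very small gain.

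**The planned analysis compares levels, not changes.** A reader might reason that recent starters worsen by 0.5-1.0 SD over the 24 weeks, and that a 20-point imbalance therefore shifts the follow-up comparison by 0.1-0.2 SD. That does not follow. If recent starters begin better and move towards long-term users, the gap in follow-up levels shrinks and so does the gain from adjustment. For the same reason, the documents do not show that such change adds noise to follow-up levels when the arms are balanced. The calculations therefore refer to a gap in the outcome as analysed, whatever its origin.

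**Scope.** The argument bears on quality of life, glucose and, less directly, lipids. Body composition is secondary, and for daily activity section 1 offers little beyond fatigue as a side effect.

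**Silence is not exclusion.** Section 5 names no stratification factor but does not rule one out, and the flow chart in section 3 could not be read in the copy reviewed. The unadjusted primary tests are explicit either way.

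**Broad eligibility is a deliberate choice in a pilot.** This is accepted, and nothing here asks for it to change.

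**Conclusion.** The point holds as one of efficiency and robustness, not validity. The plan will have time on ADT and uses it for the long-term events, yet omits it from the primary comparisons of a trial with about 20 men per arm.

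Under the assumed 20-40% of recent starters, a difference of four or more between arms occurs in 24-33% of allocations. Under an assumed gap of 0.5-1.0 SD, adjustment narrows the interval by about 2-10% with balanced arms, or about 1-9% on average without stratification. At 0.5 SD the gain is 2-3% at best. It reaches 10% only with 40% recent starters and a gap of 1 SD, and it could be smaller for follow-up levels if the groups converge. These figures concern time on ADT alone. Adjusting for the baseline value brings a separate gain, which cannot be sized because the documents give no correlation between visits.

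A reader might also infer that eligibility should be restricted by ADT duration, or that continued ADT should be required. Neither follows. Those are clinical eligibility decisions, and the statistical problem can be handled without them.

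**What to change.** - In section 7, replace the unadjusted comparisons of follow-up values of the primary outcomes with a prespecified ANCOVA, on transformed or ranked data if skewed. Include study arm, the man's baseline value and time on ADT at entry, and state the form of the time-on-ADT term (continuous or categorised) in advance.
- Report the distribution of time on ADT by arm.
- If recruitment has not started, add to section 5 that randomisation is stratified in permuted blocks by one binary time-on-ADT factor. The investigators should fix the cut-off in advance, since the documents offer no basis for a particular value. The stratum should then be reflected in the model.
- If recruitment has started, make the change to the analysis alone.

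The cost is real but small. The primary method changes from a two-sample test to a regression model, so this is more than an added term. One or two degrees of freedom are used, two randomisation lists replace one, and incomplete blocks can leave the arms slightly unequal in size. No new variable is needed, because the Cox models already require time on ADT.

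### Section 4 lets men already in a supervised exercise programme be randomised, so a control-arm man may be supervised from entry and dilute the contrast the pilot is meant to estimate

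*Combined protocol and SAP*

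**What the plan says.** **Eligibility (section 4).** The inclusion criteria are "ADT for prostate cancer, regardless of treatment duration" and "Willingness to participate in the study; signing of informed consent". The exclusions are inability for exertion or ECOG 2 or higher, high fracture risk, and not understanding Finnish.

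**Arms (section 5).** All men attend the same introductory lecture, after which "the participants are randomized 1:1 to either the supervised or non-supervised exercise group". No stratification is mentioned. The comparator is defined in one sentence: "The non-supervised group will exercise independently for 12 weeks according to the instructions given at the introductory lecture". From the first to the second control visit both arms exercise without supervision, and the second visit is meant to show "has the intervention promoted long-term change in exercise activity".

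**Purpose and size (section 3).** "The study aims to recruit 40 men on ADT for prostate cancer", and "This will be a pilot study to estimate effect sizes in Finnish population to inform further larger trial". The section adds that "no power calculation is performed yet".

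**Data on prior exercise.** Section 6 makes earlier exercise an interview topic and describes the baseline interview for a group of 10 men. Section 7 plans a baseline value of monitor-measured daily activity in MET units.

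**Analysis (section 7).** Activity is compared between arms at baseline and at the control visits by Mann-Whitney or t-test. The only covariate list belongs to the Cox model for long-term outcomes, and it does not include baseline activity.

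**The concern.** Both arms hear the same advice and both exercise, so supervision is what separates them. A man who already trains under an instructor satisfies every criterion, and nothing in the plan asks him about it or says whether he may continue. In the control arm he does not fit that arm's definition. In the supervised arm he gains less additional supervision than intended. Either way he adds less than a full contrast.

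The pilot's main product is an effect size for a larger trial, so a diluted estimate affects the thing it exists to deliver. The wrist monitor records how much a man moves, not whether someone supervised him, so the planned quantitative data would not show the dilution.

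A related and weaker issue concerns men who exercise regularly on their own. They may have less room to increase, and a man who was active before entry and is still active at the second control visit has carried on without having changed. The planned tests make no use of his entry level.

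**Working it through.** **1. Check the gap.** Each criterion in section 4 was read against current exercise. ADT status, consent, fracture risk and language have no bearing on it. The exertion/ECOG criterion removes men who cannot exercise, not men who already do. Section 5 restricts nothing outside the trial. The gap is confirmed.

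**2. No stated figure to reproduce.** The 40 men do not come from a power calculation, and no alpha, effect size, SD or dropout rate is given. Everything below is illustration under stated assumptions.

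**3. Dilution.** Let p be the share of men, equal in both arms in expectation, who contribute no contrast, and d the standardised difference in the rest.

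Expected difference = p × 0 + (1 − p) × d = (1 − p) × d

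| assumed p | fraction of d retained | result if d = 0.5 |
|---|---|---|
| 10% | 0.9 | 0.45 |
| 20% | 0.8 | 0.40 |
| 30% | 0.7 | 0.35 |

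Zero contrast is the extreme case. If these men keep part of the contrast, the loss is smaller.

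**4. Would the control arm contain such a man?** With 40 men at 1:1 there are 20 per arm. If a share q of eligible men were in supervised training, the chance of at least one in the control arm is 1 − (1 − q)^20:

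- q = 5%: 1 − 0.95^20 = 0.64
- q = 10%: 1 − 0.90^20 = 0.88
- q = 20%: 1 − 0.80^20 = 0.99

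Even a low share would probably put one man there, but one man in 20 is a share of only 5%.

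**5. Set against the pilot's precision.** The 95% confidence half-width for a difference of means at 20 per arm, without dropout, is 2.024 × √(2/20) = 0.64 SD. With d = 0.5 and p = 20%, dilution removes 0.5 − 0.4 = 0.1 SD. The pilot could not see a shift of that size in its own results, which is why the information has to be collected at entry.

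**6. Regular exercisers.** Randomisation balances them on average, but not necessarily in 40 men. If 20% were regular exercisers, the standard deviation of the between-arm difference in that share would be √(2 × 0.2 × 0.8 / 20) = √0.016 = 0.126, about 2.5 men out of 20. Unadjusted tests leave such an imbalance in the activity comparison. A model with baseline activity takes most of it out to the extent that baseline predicts follow-up.

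**The case against.** The strongest reply is that breadth of entry is a legitimate choice in a small pilot of a Finnish population, and that the plan already holds more entry data than the eligibility list suggests. Several parts of it stand.

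- **No such man is shown to exist.** A reader might infer that some control men are in fact supervised from the first day. The documents permit this but do not show it, and they give no prevalence.
- **Baseline activity is planned.** A reader might infer that the pilot could never tell dilution from a weak effect of supervision. That is too strong: results can be examined by baseline MET level, which addresses limited room to increase. It does not address outside supervision, which METs do not reveal.
- **Active men are not credited to supervision.** All comparisons are between arms, and such men are expected equally in both. The remaining issue is noise and chance imbalance.
- **The ceiling is an inference.** An active man given twice-weekly progressive sessions may still differ from an active control. Nothing in the documents supports extending a ceiling on activity to lipids, HbA1c or quality of life.
- **Sample-size inflation is conditional.** A reader might conclude that the later trial would need 1/(1 − p)² times as many men (1.23, 1.56 or 2.04 times at 10%, 20% or 30%). That excess arises only if the later trial excludes these men. If it keeps the same broad entry, the diluted effect is the right planning value.

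What the reply does not answer is that the control arm is defined by independent exercise, while the criteria admit men who do not meet that definition and no one would record it.

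**Conclusion.** The point holds in a limited form. The criteria and the definition of the control arm do not fit together for men already in supervised training, and the plan neither excludes nor counts them. The direction is dilution of the supervision contrast, not systematic confounding. Its size is unknown: 0.9 of the true difference at an assumed 10% and 0.8 at 20%, on the further assumption that these men contribute no contrast at all. The trial is not invalidated.

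A reader might also take this as grounds for excluding regular exercisers. The documents do not support that. Their reduced scope for change is not established, both arms are affected alike in expectation, and adjustment for entry activity deals with chance imbalance. The case for adjusting is therefore one of precision and interpretability; adjustment does not remove a ceiling.

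**What to change.** **Section 4.** Add that men currently in a supervised or instructor-led exercise programme are not eligible. Before randomisation, ask every man whether he is in one and how many exercise sessions he does per week.

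**Section 5.** At each control visit, record in both arms any supervised exercise taken outside the trial.

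**Section 7.** Compare daily activity at the control visits by ANCOVA with the planned baseline MET value as covariate, or a rank-based version if the data are clearly non-normal. The protocol does not say whether the monitor is worn before randomisation. If no pre-randomisation MET value is available, use the pre-randomisation sessions per week instead. Judge continued exercise at the second control visit against each man's own entry level, with the rule fixed before the first randomisation.

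**Cost.** A few otherwise eligible men are lost. Two baseline questions and one question per control visit are added. The activity comparison needs a regression model, because neither of the stated two-sample tests takes a covariate. The pilot's effect size will then apply to men not already in supervised exercise, so the larger trial should use the same criterion or allow for the difference when it is sized.
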